4.2 Study Endpoints

4.2.1 Primary Study Endpoints

The primary endpoints will be a 2% increase in RC and a 5% decrease in MC. These values are taken from (Brunfeldt et al., 2022).

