4.2.2 Secondary Study Endpoints

The secondary endpoint will be a significant relationship between the change in MC (% decrease in MC) and CSTLL with an R^2 value greater than 0.4 (Brunfeldt et al., *in review*).

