10.1 Statistical and Analytical Plans (SAP)

There will not be a formal SAP.

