10.2 Statistical Hypotheses

Primary endpoint. Exoskeletal support will increase RC in stroke participants. Paired t-test comparing RC from baseline to loading blocks.

Primary endpoint. Exoskeletal support will decrease MC in stroke participants. Paired t-test comparing MC from baseline to loading blocks.

Secondary endpoint. There will be an association between change in RC (or MC) and CST lesion load. Independent linear regressions (RC vs. CSTLL and MC vs. CSTLL).

Secondary endpoint. RC values in stroke participants will be less than RC values in healthy controls during baseline blocks (t-test). MC values in stroke participants will be greater than MC values in healthy controls during baseline blocks (t-test).

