10.4 Description of Statistical Methods

10.4.1 General Approach

This study is a repeated measures cohort design. Two groups of participants (stroke, healthy control) will perform a reaching task with and without an exoskeleton device. Primary endpoint measures will be compared within-subject to assess the effects of exoskeleton loading on coordination (kinematic: RC and muscular: MC). A between-subjects analysis will be performed to assess differences in arm control between stroke and healthy control participants.

- For descriptive statistics, we will use ranges, means, and standard deviation as appropriate. For example individual ages will be reported and further summarized with mean and standard deviation.
- For inferential statistics, we will perform two-tailed paired- and unpaired t-tests and ANOVA where appropriate. Statistical significance will be assessed at the Type-I error less than $p = 0.05$ level. See Section 10.4.2.
- Covariates will not be pre-specified
- Statistical test assumptions will be analyzed following data collection. Appropriate adjustments (e.g., normality) will be performed, such as transformation or the use of non-parametric tests.

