10.4.2 Analysis of the Primary Efficacy Endpoint(s)

Primary study objective (change in RC, MC)

- Two-way ANOVAs on RC are conducted with within-subjects factor block (baseline, loading, retention) and between-subjects factor cohort (healthy, stroke). Three-way ANOVAs on MC are performed with within-subjects factors block and muscle (deltoid, biceps) and between-subjects factor cohort.

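### The primary endpoints are stated in three ways (fixed 2% and 5% changes, stroke-only paired tests, two-cohort ANOVAs), and no text says which one decides

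*Combined protocol and SAP*

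**What the plan says.** The Protocol Summary and section 4.2.1 define the primary endpoints by size: "The primary endpoints will be a 2% increase in RC and a 5% decrease in MC". Section 4.2.1 attributes the values to the 2022 study, which section 2.1 describes as 12 healthy controls. It does not say whether the percentages are points or relative change, group means or individual changes.

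Section 10.2 lists two hypotheses labelled as primary, both about stroke participants: "Paired t-test comparing RC from baseline to loading blocks" and "Paired t-test comparing MC from baseline to loading blocks". Neither test carries a 2% or 5% margin.

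Section 10.4.2, under the primary efficacy heading, gives something else. For RC: "Two-way ANOVAs on RC are conducted with within-subjects factor block (baseline, loading, retention) and between-subjects factor cohort (healthy, stroke". For MC: "Three-way ANOVAs on MC are performed with within-subjects factors block and muscle (deltoid, biceps) and between-subjects factor cohort". It names no deciding term or contrast.

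On choosing between tests, section 10.4.1 offers "we will perform two-tailed paired- and unpaired t-tests and ANOVA where appropriate". It also says that the primary measures are compared within subjects to assess loading, and that a between-subjects analysis assesses differences between the cohorts. Section 10.1 adds "There will not be a formal SAP", so no later planned document will settle the matter.

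**The concern.** The stated hypothesis concerns stroke participants, but the protocol gives three ways to reach a conclusion about it. A mean RC change of 2 points that is not significant meets the section 4.2.1 wording and fails the 10.2 test. A significant change of 1.5 points does the reverse. A significant ANOVA block effect could be reported under the primary efficacy heading although the stroke group did not change, because that term averages over both cohorts.

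The last case is not far-fetched. Section 2.1 reports an effect on limb coordination in healthy controls. Section 2.2.1 reports no significant group-level change in RC or MC in 14 stroke participants.

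The study is unmasked (10.6.1), and one investigator both collects and analyses the data (16.1). That is a reason to fix the deciding analysis before any data are seen.

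**Working it through.** **Inputs.** From the documents: values of 2% and 5% (4.2.1); 12 participants per cohort (Protocol Summary); two-sided 0.05 (10.4.1); f = 0.25 to 0.3, power 0.8, total 20 to 28 (10.5). Assumed: 2% and 5% are group-mean changes in points; data are normal; RC change SDs are 2, 3.15, 4 and 8 points, since the documents give none.

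**1. The plan's own sample size.** Treat it as a repeated-measures ANOVA with two groups and m = 3 blocks, with assumed correlation ρ = 0.5 and sphericity. Then λ = f²·N·m/(1 − ρ), with df = 2 and 2(N − 2).
- f = 0.25, N = 28: λ = 0.0625 × 28 × 3 / 0.5 = 10.5, df 2 and 52, power 0.812.
- f = 0.30, N = 20: λ = 0.09 × 20 × 3 / 0.5 = 10.8, df 2 and 36, power 0.812.

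Both ends of the 20 to 28 range are reproduced, and the block and interaction terms give the same N. At the same ρ, two measurements would give 34 and 24. The sizing therefore fits the 10.4.2 layout, not the 10.2 paired test.

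**2. Fixed value against paired test.** With n = 12, significance needs a mean change of at least t(0.975, 11)/√12 = 2.201/3.464 = 0.635 times the observed SD of the change. The two cutoffs coincide at:
- RC: 2/0.635 = 3.15 points
- MC: 5/0.635 = 7.87 points

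Below those SDs, a change smaller than the stated value can be significant. At RC SD 2 the cutoff is 1.27 points. Above them, a change that reaches the value can be non-significant. At RC SD 4 the cutoff is 2.54 points.

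**3. How often they differ for RC (illustrative).** The chance of reaching 2 points when nothing changes is 1 − Φ(2√12/SD). Disagreement is by simulation.

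| RC change SD | True change 2: value and paired test disagree | True change 0: value reached | True change 0: paired test significant upward |
|---|---|---|---|
| 2 | 38% | 0.03% | 2.5% |
| 3.15 | 14% | 1.4% | 2.5% |
| 4 | 18% | 4.2% | 2.5% |
| 8 | 38% | 19% | 2.5% |

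Disagreement remains at a true SD of 3.15 because the observed SD varies between trials. The same figures hold for MC at SDs 2.5 times as large.

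**4. ANOVA block effect against the stroke question (illustrative).** Assume controls change by 2 points and stroke by 0, retention equals baseline, and variances and correlations are equal.

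| RC change SD | Block effect significant, interaction not | Stroke paired test significant upward |
|---|---|---|
| 2 | about 21% | 2.5% |
| 3.15 | about 21% | 2.5% |
| 4 | about 16% | 2.5% |
| 8 | about 8% | 2.5% |

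**5. Power of the paired test.** With 12 stroke participants, noncentral t gives 80% power at a change of 0.89 SD. If only the loading block differs, by d, then f = d(√2/3)/σ. At ρ = 0.5 the SD of the change equals σ, so f = 0.25 to 0.3 means a change of 0.53 to 0.64 SD, and power is about 39% to 52%.

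**The case against.** The strongest reply is that these are complementary analyses and not rival rules. Section 10.4.1 gives the within-subject comparison to the primary measures and a between-subjects analysis to the cohort difference. Section 3.1 asks both questions, and 10.2 attaches one population, one contrast and one test to each primary hypothesis. This largely stands: a reader can infer that the stroke contrast is the main question, and it would be wrong to call the intent unreadable. It does not settle the conflict, because 4.2.1 words the sizes as the endpoints themselves and 10.4.2 places the ANOVAs under the primary efficacy heading.

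The 2% and 5% could be expected effects. That is possible, but the text does not say so, and 4.2.2 shows that a size limit can be part of an endpoint here: "a significant relationship between the change in MC (% decrease in MC) and CSTLL with an R^2 value greater than 0.4". From that, a reader might infer that the primary endpoints also need significance and size together. The documents do not support this. The combination is written for the secondary endpoint only, so success rates computed under such a joint rule say nothing about this plan.

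A reader might also take the block effect's overall rate in step 4 (about 69%, 32%, 21% and 9%) as the rate of misleading conclusions. That overstates it. No text makes the block term decisive, and in many of those trials the interaction is also significant and shows that the cohorts differ. Zero change in stroke is itself an assumption: 2.2.1 reports a non-significant change, and 2.2.3 says that the 50% level changed arm coordination in both earlier studies.

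Keeping the ANOVA with a named stroke contrast from baseline to loading would stay closer to 10.5. It is a fair alternative, but the paired test is already written into 10.2. Lastly, this is a single-session pilot, which limits the consequence.

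**Conclusion.** The concern holds as a conflict between stated rules. The primary endpoints appear as fixed changes from healthy adults, as stroke-only paired tests that use neither value, and as two-cohort ANOVAs with no deciding term. The text leans towards the within-stroke contrast but never ranks the three.

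That they can disagree follows from n = 12 and the stated alpha: the value and the paired test share a cutoff only at an SD of about 3.15 points (RC) or 7.87 points (MC), if the percentages are group-mean points. How often they disagree depends on SDs that the documents do not give, so the simulated rates show possibility and not likelihood. The match of 10.5 to the ANOVA layout rests on an assumed correlation of 0.5.

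This should be corrected before data are seen. It does not call the design into question.

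**What to change.** - **Summary and 4.2.1:** define the primary endpoints as the stroke group's mean change from baseline to loading in RC and in MC, with units. Each is judged by its 10.2 paired test at two-sided 0.05 and reported with a 95% confidence interval. Show 2% and 5% beside the interval as healthy-adult reference values only.
- **10.4.2:** state that the ANOVAs serve the cohort comparison in 3.1, through the block-by-cohort term, and retention. State that the block main effect does not decide the stroke hypothesis.
- **10.5:** state that the f-based calculation applies to the ANOVA, and that the paired test with 12 stroke participants has 80% power only for a change of about 0.89 SD.

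No new data or participants are needed. The team gives up a fixed numeric target, so the confidence interval has to carry the size of the effect. The power that it must state for the deciding test is less favourable than 10.5 now suggests, which a pilot can acknowledge.

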4.2.2 Secondary Study Endpoints

The secondary endpoint will be a significant relationship between the change in MC (% decrease in MC) and CSTLL with an R^2 value greater than 0.4 (Brunfeldt et al., *in review*).

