Title	A pilot proof of concept, single site study to assess the effect of exoskeletal support on motor control strategies in individuals with stroke
Short Title	Exoskeletal support in stroke
Brief Summary	This interventional study will measure motor performance, including 3D movement analysis and muscle activity, in response to exoskeleton assistance. The cohort design will compare stroke patients to healthy controls. Data collection will be conducted in a single, 2-hour session. We will also access stroke patients' brain MRIs that were obtained as standard of care during acute admission for stroke.
Phase	Pilot
Objectives	The primary objective is to examine in a VR environment whether additional gravity compensation from exoskeletal support will improve bimanual coordination in stroke patients. A second primary objective is to determine intervention effects on muscle control processes underlying bimanual coordination. As a secondary objective, we aim to correlate these measures with measures of stroke lesion characteristics.
Methodology	Cohort design
Endpoint	The primary endpoints will be a 2% increase in RC and a 5% decrease in MC. The secondary endpoint will be a significant relationship between the change in MC (% decrease in MC) and CSTLL with an R^2 value greater than 0.4
Study Duration	12 months
Participant Duration	One, 2-hour session
Duration of IP administration	Approximate 15 minutes
Population	24 participants; 12 with history of stroke more than 6-months prior to enrollment, 12 healthy age- and gender-matched controls. Males and females 18-years old and older from with and without diagnosis of stroke.
Study Site	Single-center (NYULMC)
Number of participants	24
Description of Study Agent/Procedure	We use a custom designed and built exoskeleton device that applies a torque to both shoulders. Torque values do not exceed 50% of the torque due to gravity. The device is mounted to a testing chair and attached to the participant using Velcro straps.
Reference Therapy	N/A
Key Procedures	No clinical procedures are required
Statistical Analysis	Inferential group statistics (t-test, mixed design ANOVA); correlation, linear regression

Schematic of Study Design

1 Key Roles

Principal Investigator

[name], Associate Professor
NYU Grossman School of Medicine
[name]
T [contact] (ACC)
[contact]

Study Investigator

[name], Postdoc
[name]
[contact]
[contact]

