10.4.3 Analysis of the Secondary Endpoint(s)

Secondary study objective (Motor performance vs. CST lesion load)

- We first perform linear regressions to assess the relationship between lesion load and Upper Extremity Fugl-Meyer (UE-FM). Coefficient of determination (R^2) values ranging from 0.2 to 0.7 have been previously reported (Cassidy et al., 2018; Feng et al., 2015; Lin et al., 2019; Zhu et al., 2010).
- We regress lesion load into the change in RC (ΔRC), change in MC (ΔMC), and tradeoff slope. Any motor performance measures that fail to achieve R^2 values greater than 0.2 when regressed to CST lesion load will be discarded from further analysis.

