10.5 Sample Size

Study Hypotheses: (Primary study objective)

- A power analysis using a moderate effect size (Cohen's $f = 0.25 - 0.3$) on MC, power of 0.8, and significance level of 0.05 suggests a total sample of 20-28 participants (10-14 per group). This is consistent with previous work using shared cursor tasks in stroke (Brunfeldt et al., 2022; Ranganathan et al., 2019).

Study Hypotheses: (Secondary study objective)

- An *a priori* power analysis with an effect size $f^2 = 0.7-0.9$, a power of $1-\beta = 0.8$ and error probability $\alpha = 0.05$ results in a target sample size of 12-14 participants. The estimated effect size was directly calculated from a Partial $R^2 = 0.4648$ using data from a feasibility study currently in preparation for publication. This R^2 value was taken from the relationship between lesion load and the change in MC from baseline to loading conditions.

Assumptions used in calculations:

- Assumed normal distribution, or corrected to normal distribution (e.g., via log-transform)
- We plan to enroll 30 participants, with between 6-8 stroke participants not meeting inclusion/exclusion criteria. The final $N = 12$ endpoint accounts for these dropouts.
- Data from withdrawn participants will not be included in the final dataset. Only those who complete all procedures will be included in the final analyses.

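### The secondary endpoint requires an observed R² above 0.4, but the 80% power covers only p<0.05; at N=12 the full rule has about 73% power, and the 0.2 discard rule inflates retained R² values

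*Combined protocol and SAP*

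**What the plan says.** The Protocol Summary and Section 4.2.2 give the secondary endpoint as "a significant relationship between the change in MC (% decrease in MC) and CSTLL with an R^2 value greater than 0.4". MC is muscle contribution and CSTLL is corticospinal tract lesion load. Read literally, this is a joint condition: significance and an observed R² above 0.4.

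Section 10.5 sizes the secondary objective with f² = 0.7-0.9, power 0.8 and α = 0.05, which it says "results in a target sample size of 12-14 participants". On the source of the effect it states: "The estimated effect size was directly calculated from a Partial $R^2 = 0.4648$ using data from a feasibility study". That R² is for lesion load against change in MC, the same relationship as the endpoint. The section then fixes the number: "The final $N = 12$ endpoint accounts for these dropouts". It does not mention the 0.4 threshold.

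Section 10.2 states the hypothesis as an association only, tested by separate linear regressions of RC and MC on CSTLL, with no R² threshold. Section 10.4.1 says that covariates will not be pre-specified.

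Section 10.4.3 regresses three measures on lesion load (change in RC, change in MC and tradeoff slope). Measures that "fail to achieve R^2 values greater than 0.2 when regressed to CST lesion load will be discarded from further analysis".

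**The concern.** The endpoint and the power statement describe different events. Someone reading 10.5 would expect an 80% chance of meeting the secondary endpoint if the planning effect is true. That holds only if the 0.4 requirement is no stricter than significance. With a threshold of 0.4 and an assumed true value of 0.4648, an observed R² in a sample of 12 could easily fall on the wrong side. If so, the study could find a significant association of roughly the expected size and still miss its endpoint.

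The 0.2 rule raises a second, separate question. It selects measures on the same statistic that is then reported. If only the survivors are carried forward, a weak association with lesion load will look stronger than it is.

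**Working it through.** **Inputs.** From 10.5: partial R² = 0.4648, f² range 0.7-0.9, power 0.8, α = 0.05, final N = 12. From 10.2 and 10.4.1: one predictor and no pre-specified covariates, so 1 and N−2 degrees of freedom. From 4.2.2: observed R² > 0.4. From 10.4.3: discard unless R² > 0.2.

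**Step 1: reproduce the plan's figure.** f² = 0.4648 / (1 − 0.4648) = 0.4648 / 0.5352 = 0.868, inside the stated range. Power is the upper tail of a noncentral F(1, N−2) with noncentrality λ = f²·N. The smallest N with at least 80% power at p<0.05 is:

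- f² = 0.7: N = 14 (81.9%)
- f² = 0.868: N = 12 (82.8%)
- f² = 0.9: N = 12 (84.1%)

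This is exactly the stated 12-14, so the 80% in 10.5 is power for significance alone. A one-sided test would give 9-11 and does not match.

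**Step 2: find the binding condition at N = 12.** The critical F(1,10) at 0.05 is 4.965, so significance needs R² > 4.965 / (4.965 + 10) = 0.332. An R² of 0.4 corresponds to F = (0.4/0.6) × 10 = 6.67, p = 0.027. The 0.4 cut is therefore the stricter condition, and the endpoint is met exactly when R² > 0.4.

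**Step 3: power for the endpoint as written.** Same noncentral F, with the critical value raised to (0.4/0.6)(N−2):

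| f² (true R²) | p<0.05, N=12 | p<0.05 and R²>0.4, N=12 | p<0.05 and R²>0.4, N=14 |
|---|---|---|---|
| 0.7 (0.412) | 74.3% | 63.1% | 62.4% |
| 0.868 (0.4648) | 82.8% | 73.2% | 73.4% |
| 0.9 (0.474) | 84.1% | 74.9% | 75.1% |

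Two more participants make almost no difference, because the cut lies close to the assumed truth. For 80% power on the full rule, N would have to be 52 at R² = 0.4648 and 37 at f² = 0.9. At f² = 0.7, N = 399 still gives only 65.3%. The table also shows that at the low end of the plan's range, N = 12 gives 74% even for p<0.05 alone.

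**Step 4: sensitivity to the model.** The calculation above holds the predictor fixed. Lesion load is observed, not set by design. If it is treated as a random normal variable (an assumption), simulation with 1,000,000 runs at N = 12 and R² = 0.4648 gives 74% for p<0.05 and 65% for the full rule. Over f² = 0.7-0.9 the full rule has 56-66%. The cut costs about 10 points in either model.

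**Step 5: the 0.2 discard rule at N = 12.** R² = 0.2 gives F = (0.2/0.8) × 10 = 2.5, p = 0.145. Any result at or below 0.2 already fails the endpoint, so the rule takes no power from it. Its effect on the average R² in the random-predictor simulation is:

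| True R² | Mean R², all results | Mean R², retained results | Share retained |
|---|---|---|---|
| 0.4648 | 0.47 | 0.52 | 88% |
| 0.2 | 0.25 | 0.40 | 53% |
| 0 | 0.09 | 0.32 | 14.5% |

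At the planning effect, 38% of retained values still lie below the truth, so the bias concerns the average and not every result. With a fixed predictor, the mean goes from 0.511 to 0.534 at the planning effect and from 0.265 to 0.397 at a true R² of 0.2.

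**The case against.** **No calculation is wrong.** The 12-14 in 10.5 is correct for the hypothesis in 10.2, which has no R² threshold. This is so. The fault is that 4.2.2 and the Protocol Summary add a condition that neither 10.2 nor 10.5 carries.

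**The 0.4 may be a benchmark.** The endpoints in Section 4.2 are written as values expected from earlier studies, and no decision is tied to passing or failing. That reading is possible, but the text of 4.2.2 makes the threshold part of the endpoint. If a benchmark is meant, the text should say so.

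**The planning value is a partial R².** Such a value may come from a model with other terms, and it need not equal the simple R² in a one-predictor regression. This caveat stands but is minor, because the plan itself converts the value to the f² that yields its N.

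**The consequence is small.** This is a pilot, the endpoint is secondary, and the effect comes from a feasibility study, so 80% against 73% lies well within the uncertainty of the planning value. That is fair as to weight. It does not justify stating a power and a success rule that do not match.

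**Dropping the 0.4 cut loosens the endpoint.** At N = 12 the cut acts as a two-sided α of about 0.027. Replacing it with p<0.05 nearly doubles the false-positive rate. This is correct, and the trade-off should be stated if that option is chosen.

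**The discard rule may do little harm.** The text says discarded from further analysis, not unreported, and the bias at the planning effect is small. Both points stand. The inflation is material only if the true association is well below the planning value, which a pilot cannot rule out.

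**Conclusion.** The concern holds on both points.

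1. The 80% power in 10.5 applies to p<0.05 only. For the endpoint in 4.2.2, power at N = 12 is about 73% at R² = 0.4648 and 63-75% over the plan's f² range. These figures use the fixed-predictor model that reproduces the plan's N and take the partial R² as the simple R². With a random normal predictor the figure at R² = 0.4648 is about 65%, so 73% is the favourable value. Moving to N = 14 does not change the conclusion.
2. The 0.2 rule is a data-driven filter that raises the average retained R². The rise is 0.02-0.05 at the planning effect, depending on the model. At a true R² of 0.2, the retained values average 0.40, which is the endpoint's own threshold.

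As this is a secondary endpoint of a pilot, the points should be corrected but do not undermine the study.

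**What to change.** **Endpoint and power: choose one option, and make the Protocol Summary, 4.2.2, 10.2 and 10.5 agree.**

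- Keep the 0.4 requirement. State in 10.5 that the 80% refers to p<0.05 only. Add the power of the full rule at N = 12 (about 73% with a fixed predictor and 65% with a random one, at R² = 0.4648), and the 74% for p<0.05 at f² = 0.7. Add the threshold to 10.2.
- Or define success in 4.2.2 as the two-sided p<0.05 test of the slope of change in MC on CSTLL. Report the slope and R² with 95% confidence intervals and keep 0.4 as a descriptive benchmark. Acknowledge that this moves the effective α at N = 12 from about 0.027 to 0.05.

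**Discard rule.** Delete it from 10.4.3. Report the regressions for change in RC, change in MC and tradeoff slope whatever their R², with change in MC named as the endpoint measure.

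**Cost.** Wording in the Protocol Summary, 4.2.2, 10.2, 10.4.3 and 10.5. No extra participants, measurements or analyses are needed, since all three regressions are already planned. Enlarging the study to meet the 0.4 rule with 80% power is not proposed.
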